## 9 Endpoints and Assessment Methods

### 9.1 Primary Endpoints and Assessment Methods

#### 9.1.1 Immunogenicity

##### 9.1.1.1 Immunogenicity Endpoints

The primary endpoints for the evaluation of immunogenicity are:

Vaccine seroresponse of meningococcal serogroups A, C, Y, and W measured by hSBA assessed at baseline (D0, before vaccination) and 30 days after vaccination

##### 9.1.1.2 Immunogenicity Assessment Methods

[Redacted text block]

[Redacted text block]

[Redacted text block]

### 9.1.2 Safety

There are no primary objectives for safety.

### 9.1.3 Efficacy

No clinical efficacy data will be obtained in the trial.

## 9.2 Secondary Endpoints and Assessment Methods

### 9.2.1 Immunogenicity

#### 9.2.1.1 Immunogenicity Endpoints

The secondary endpoints for immunogenicity are:

- 1) GMTs against meningococcal serogroups A, C, Y, and W measured by hSBA assessed at 30 days (+14 days) after vaccination with MenACYW conjugate vaccine and Menomune® – A/C/Y/W-135

#### 9.2.1.2 Immunogenicity Assessment Methods

The immunogenicity assessment method for the secondary endpoints for hSBA is the same as that presented in [Section 9.1.1.2](#).

### 9.2.2 Safety

There are no secondary objectives for safety.

### 9.2.3 Efficacy

No clinical efficacy data will be obtained in the trial.

## 9.3 Observational Endpoints and Assessment Methods

### 9.3.1 Immunogenicity

#### 9.3.1.1 Immunogenicity Endpoints

Antibody titers against meningococcal serogroups A, C, Y, and W measured by hSBA and rSBA before and 30 days (+14 days) after vaccination with MenACYW conjugate vaccine or Menomune® – A/C/Y/W-135

### 9.3.1.2 Immunogenicity Assessment Methods

[REDACTED]

#### *Antibodies to Meningococcal Antigen (rSBA Method)*

### 9.3.2 Safety

#### 9.3.2.1 Safety Definitions

The following definitions are taken from the ICH E2A Guideline for Clinical Safety Data Management: Definitions and Standards for Expedited Reporting.

##### *Adverse Event (AE):*

An AE is any untoward medical occurrence in a patient or clinical investigation subject administered a pharmaceutical product and which does not necessarily have to have a causal relationship with this treatment. An AE can therefore be any unfavorable and unintended sign (including an abnormal laboratory finding, for example), symptom or disease temporally associated with the use of a medicinal product, whether or not considered related to the medicinal product.

Therefore an AE may be:

- A new illness
- The worsening of a concomitant illness

---

a T60: Time of incubation duration of 60 minutes

- An effect of the vaccination, including the comparator
- A combination of the above

All AEs include serious and non-serious AEs.

Surgical procedures are not AEs; they are the action taken to treat a medical condition. It is the condition leading to the action taken that is the AE (if it occurs during the trial period).

Pre-existing medical conditions are not to be reported as AEs. However, if a pre-existing condition worsens in frequency or intensity, or if in the assessment of the treating physician there is a change in its clinical significance, this change should be reported as an AE (exacerbation). This applies equally to recurring episodes of pre-existing conditions (e.g., asthma) if the frequency or intensity increases post-vaccination.

***Serious Adverse Event (SAE):***

*Serious* and *severe* are not synonymous. The term *severe* is often used to describe the intensity of a specific event as corresponding to Grade 3. This is not the same as *serious* which is based on patient / event outcome or action criteria usually associated with events that pose a threat to a patient's life or functioning. Seriousness, not severity, serves as a guide for defining regulatory reporting obligations.

An SAE is any untoward medical occurrence that at any dose

- Results in death
- Is life-threateninga
- Requires inpatient hospitalization or prolongation of existing hospitalizationb
- Results in persistent or significant disability / incapacityc
- Is a congenital anomaly / birth defect
- Is an important medical eventd

---

a The term "life-threatening" refers to an event in which the subject was at risk of death at the time of the event; it does not refer to an event which hypothetically might have caused death if it were more severe.

b All medical events leading to hospitalizations will be recorded and reported as SAEs, with the exception of: hospitalization planned before inclusion into the study or out-patient treatment with no hospitalization.

c "Persistent or significant disability or incapacity" means that there is a substantial disruption of a person's ability to carry out normal life functions.

d Medical and scientific judgment should be exercised in deciding whether expedited reporting is appropriate in other situations, such as important medical events that may not be immediately life-threatening or result in death or hospitalization but may jeopardize the health of the subject or may require intervention to prevent one of the other outcomes listed in the definition above. These should also usually be considered serious. Examples of such events include allergic bronchospasm requiring intensive treatment in an emergency room or at home, blood dyscrasias or convulsions that do not result in inpatient hospitalization, or the development of drug dependency or drug abuse, GBS, new onset diabetes, or autoimmune disease.

***Adverse Reaction:***

All noxious and unintended responses to a medicinal product related to any dose should be considered adverse reactions (AR).

(The phrase “responses to a medicinal product” means that a causal relationship between a medicinal product and an AE is at least a reasonable possibility)

***Unexpected Adverse Reaction (UAR):***

An unexpected adverse reaction is an AR, the nature or severity of which is not consistent with the applicable product information (e.g., Investigator’s Brochure for an unapproved investigational medicinal product).

The following additional definitions are used by Sanofi Pasteur:

***Solicited Reaction:***

A solicited reaction is an event that is prelisted in the CRF. The assessment of these AEs post-vaccination is mandatory. A solicited reaction is defined by a combination of:

- Symptom and
- Onset post-vaccination

e.g., injection site pain between D0 and D07 after vaccination, or headache between D0 and D07

A solicited reaction is therefore an AR observed and reported under the conditions (symptom and onset) prelisted (i.e., solicited) in the CRF and considered as related to vaccination.

***Unsolicited AE / AR:***

An unsolicited AE is an observed AE that does not fulfill the conditions prelisted in the CRF in terms of diagnosis and / or onset post-vaccination, i.e., excluding solicited reactions, e.g., if headache between D0 and D7 is a solicited reaction (i.e., prelisted in the CRF), then a headache starting on D7 is a solicited reaction, whereas headache starting on D8 post-vaccination is an unsolicited AE.

An unsolicited non-serious AE is an unsolicited AE excluding SAEs.

***Injection Site Reaction:***

An injection site reactiona is an AR at and around the injection site. Injection site reactions are commonly inflammatory reactions.

***Systemic AE:***

Systemic AEs are all AEs that are not injection site reactions. They therefore include systemic manifestations such as headache, fever, as well as localized or topical manifestations that are not

---

a All injection site AEs are considered to be related to vaccination and are therefore all *injection site reactions*.

associated with the vaccination site, e.g., erythema that is localized but that is not at the injection site.

#### ***Medically-Attended Adverse Events (MAAEs):***

An MAAE is defined, for the purpose of this study, as a new onset of a condition that prompts the subject to seek unplanned medical advice at a physician's office or Emergency Department.

This definition excludes pre-planned medical office visits for routine check-ups or follow-up visits of chronic conditions with an onset prior to entry in the study. Physician contact made over the phone or by email will be considered a physician office visit for the purpose of MAAE collection.

The outcome of the physician contact (whether it results in a prescription or not) will not be considered as a basis for reporting the event as an MAAE and all contacts should be reported. Sufficient data should be collected for the event to allow an assessment of the causality and diagnosis, if possible.

#### **9.3.2.2 Safety Endpoints**

The observational endpoints for the evaluation of safety are:

- Occurrence, nature (Medical Dictionary for Regulatory Activities [MedDRA] preferred term), duration, intensity, and relationship to vaccination of any unsolicited systemic AEs reported in the 30 minutes after vaccination.
- Occurrence, time to onset, number of days of occurrence, intensity, action taken, and whether the reaction led to early termination from the study, of solicited (prelisted in the subject's DC and electronic case report form [CRF]) injection site reactions occurring up to 7 days after vaccination.
- Occurrence, time to onset, number of days of occurrence, intensity, action taken, and whether the reaction led to early termination from the study, of solicited (prelisted in the subject's DC and CRF) systemic reactions occurring up to 7 days after vaccination.
- Occurrence, nature (MedDRA preferred term), time to onset, duration, intensity, action taken, relationship to vaccination (for systemic AEs only), and whether the event led to early termination from the study, of unsolicited AEs occurring up to Visit 2.
- Occurrence, nature (MedDRA preferred term), time to onset, duration, seriousness criteria, relationship to vaccination, outcome, and whether the SAE led to early termination from the study, of SAEs throughout the trial.
- Occurrence, nature (MedDRA preferred term), time to onset, duration, seriousness, relationship to vaccination, and outcome for MAAEs from Visit 2 to the 6-month follow-up contact. MAAEs will be collected as unsolicited AEs up to Visit 2.

#### **9.3.2.3 Safety Assessment Methods**

At Visit 2, the Investigator or a delegate will ask the subject about any solicited reactions and unsolicited AEs recorded in the DC, as well as about any other AEs that may have occurred since

the previous visit. All relevant data will be transcribed into the CRF according to the instructions provided by the Sponsor.

#### 9.3.2.3.1 Immediate Post-vaccination Surveillance Period

Subjects will be kept under observation for 30 minutes after vaccination to ensure their safety. The post-vaccination surveillance should be documented in the source document. Any AE that occurs during this period will be noted on the source document and recorded in the CRF, as follows:

- Any unsolicited systemic AE occurring during the first 30 minutes post-vaccination will be recorded on the CRF as immediate unsolicited systemic AE.
- Solicited and unsolicited injection site reactions and solicited systemic reactions will be recorded and analyzed as starting on the day of vaccination.
- Any SAE occurred during the first 30 minutes post-vaccination will be reported in the same way as any other SAE and to the Sponsor, according to the procedures described in [Section 10](#).

#### 9.3.2.3.2 Reactogenicity (Solicited Reactions from Day 0 to Day 7 after Vaccination)

After vaccination, subjects will be provided with a safety DC, a digital thermometer, and a flexible ruler, and will be instructed how to use them. The following items will be recorded by the subjects in the DC on the day of vaccination and for the next 7 days (i.e., D0 to D07) until resolution:

- Daily temperature, with the route by which it was taken
- Daily measurement or intensity grade of all other solicited injection site and systemic reactions
- Action taken for each event, if any (e.g., medication)

The action taken by the subject to treat any **solicited reactions** will be classified in the CRF using the following scale:

- 0: None
- 1: Medication (self-medication with an existing prescription or over-the-counter medication)
- 2: Health care provider contact (no new medication prescribed)
- 3: Health care provider contact and prescription of a new medication (health care provider instructed subject to take a new medication, either an over-the-counter medication or one requiring a written prescription)
- 4: Hospitalization (inpatient)

Subjects will be contacted by telephone 8 days after vaccination to remind them to record all safety information in the DC.

If the timing of the telephone call should fall on a weekend or a holiday, the call should be made on the next business day. If contact is not made on the designated day, study staff will continue

calling until contact is made. Every telephone attempt and its outcome will be documented in the source document.

[Table 9.1](#) and [Table 9.2](#) present, respectively, the injection site reactions and systemic reactions that are prelisted in the DCs and CRF, together with the intensity scales.

**Table 9.1: Solicited injection site reactions: terminology, definitions, and intensity scales**

CRF term (MedDRA lowest level term [LLT])	Injection site pain	Injection site erythema	Injection site swelling
DC term	Pain	Redness	Swelling
Definition		Presence of a redness including the approximate point of needle entry	Swelling at or near the injection site Swelling or edema is caused by a fluid infiltration in tissue or cavity and, depending on the space available for the fluid to disperse, swelling may be either soft (typically) or firm (less typical) to touch and thus can be best described by looking at the size of the swelling
Intensity scale*	Grade 1: No interference with activity Grade 2: Some interference with activity Grade 3: Significant; prevents daily activity	Grade 1: $\geq 25$ to $\leq 50$ mm Grade 2: $\geq 51$ to $\leq 100$ mm Grade 3: $> 100$ mm	Grade 1: $\geq 25$ to $\leq 50$ mm Grade 2: $\geq 51$ to $\leq 100$ mm Grade 3: $> 100$ mm

\* For the subjective reaction of pain, subjects will record the intensity level (Grade 1, 2, or 3) in the diary card. For the measurable reactions of redness and swelling, they will record just the size of the reaction, and the classification as Grade 1, 2, or 3 will be assigned at the time of the statistical analysis

**Table 9.2: Solicited systemic reactions: terminology, definitions, and intensity scales**

CRF term (MedDRA LLT)	Fever	Headache	Malaise	Myalgia
DC term	Temperature	Headache	Feeling unwell	Muscle aches and pains
Definition	Elevation of temperature to $\geq 100.4^{\circ}\text{F}$ ( $\geq 38.0^{\circ}\text{C}$ )	Pain or discomfort in the head or scalp. Does not include migraine.	General ill feeling. Malaise is a generalized feeling of discomfort, illness, or lack of well-being that can be associated with a disease state. It can be accompanied by a sensation of exhaustion or inadequate energy to accomplish usual activities.	Muscle aches and pains are common and can involve more than one muscle at the same time. Muscle pain can also involve the soft tissues that surround muscles. These structures, which are often referred to as connective tissues, include ligaments, tendons, and fascia (thick bands of tendons).  Does not apply to muscle pain at the injection site which should be reported as injection site pain.
Intensity scale*	Grade 1: $\geq 100.4^{\circ}\text{F}$ to $\leq 101.1^{\circ}\text{F}$ , or $\geq 38.0^{\circ}\text{C}$ to $\leq 38.4^{\circ}\text{C}$ Grade 2: $\geq 101.2^{\circ}\text{F}$ to $\leq 102.0^{\circ}\text{F}$ or $\geq 38.5^{\circ}\text{C}$ to $\leq 38.9^{\circ}\text{C}$ Grade 3: $\geq 102.1^{\circ}\text{F}$ or $\geq 39.0^{\circ}\text{C}$	Grade 1: No interference with activity  Grade 2: Some interference with activity  Grade 3: Significant; prevents daily activity	Grade 1: No interference with activity  Grade 2: Some interference with activity  Grade 3: Significant; prevents daily activity	Grade 1: No interference with activity  Grade 2: Some interference with activity  Grade 3: Significant; prevents daily activity

\* For all reactions but fever, subjects or parents / legally acceptable representatives will record the intensity level (Grade 1, 2, or 3) in the diary card. For fever, they will record the body temperature, and the classification as Grade 1, 2, or 3 will be assigned at the time of the statistical analysis.

***Important notes for the accurate assessment of temperature:***

Subjects are to measure body temperature once per day, preferably always at the same time. The optimal time for measurement is the evening, when body temperature is the highest. Temperature is also to be measured at the time of any apparent fever. The observed daily temperature and the route of measurement are to be recorded in the DC, and the highest temperature will be recorded by the site in the CRF. The preferred route for this trial is oral. Pre-vaccination temperature is also systematically collected by the Investigator in the source document. Tympanic thermometers must not be used.

**9.3.2.3.3 Unsolicited Non-serious Adverse Events from Day 0 to Day 30 after Vaccination**

In addition to recording solicited reactions, subjects will be instructed to record any other medical events that may occur during the 30-day period after vaccination. Space will be provided in the DC for this purpose.

For each unsolicited non-serious AE, the following information is to be recorded:

- Start and stop datesa
- Intensity of the event:
  - For measurable unsolicited non-serious AEs that are part of the list of solicited reactions, the size of the AE as well as the temperature for fever will be collected and analyzed based on the corresponding scale used for solicited reactions (see [Table 9.1](#) and [Table 9.2](#))
  - Other unsolicited non-serious AEs will be classified according to the following intensity scale:
    - Grade 1: No interference with activity
    - Grade 2: Some interference with activity
    - Grade 3: Significant; prevents daily activity
- Action taken for each AE, if any (e.g., medication)

The action taken by the subject to treat any **unsolicited AEs** will be classified in the CRF using the following scale:

- 0: None
- 1: Medication (self-medication with an existing prescription or over-the-counter medication)
- 2: Health care provider contact (no new medication prescribed)
- 3: Health care provider contact and prescription of a new medication (health care provider instructed subject to take a new medication, either an over-the-counter medication or one requiring a written prescription)

---

a The stop date of all related AEs will be actively solicited. For other events, the investigator will provide the stop date when it becomes available. AEs for which no stop date was obtained during the course of the trial will be considered as ongoing at the end of the trial.

- Whether the AE led to discontinuation
- Whether the AE was related to vaccination (for unsolicited systemic AEs)

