- 1) Record relevant information concerning the subject's health status on the telephone contact form. If an SAE occurred, follow the instructions in [Section 10](#) for reporting it.
- 2) Remind the subject to do the following:
  - Complete the D0 to D07 pages of the DC
  - Complete the remaining pages of the DC, and bring them to Visit 2.
  - Notify the site in case of an SAE.

Visit 2 (30 [+14] days after Visit 1): Collection of Safety Information and Blood Sample

- 1) Review the pages of the DC with the subject, including any AEs, medications, or therapy that occurred since vaccination.
- 2) Review the temporary contraindications for blood sampling (see [Section 5.2.8](#)).
- 3) Obtain the second blood sample (see [Section 7.1](#) for detailed instructions regarding the handling of blood samples).
- 4) Give the subject an MA.
- 5) Complete the termination record of the CRF.
- 6) If the subject does not return for Visit 2, and the DC is not received at the site, site personnel will contact the subject by telephone. During the telephone call, the subject will be reminded to return the DC to the study site. Telephone calls will be documented on the Telephone / Interview Record. If the study personnel are unable to contact the subject with 3 attempts, the study personnel will follow instructions given in [Section 5.2.10](#).

Safety Follow-up Telephone Call (180 [+14] days after Visit 1): Collection of SAEs and MAAEs

Review the MA and ask the subject if he/she has experienced any SAE in the time since vaccination that has not been reported to the study personnel and / or MAAE.

- If an SAE has occurred, follow the instructions in [Section 10](#) for reporting it.
- If an MAAE has occurred, follow the instructions in the Operating Guidelines.

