### ***SAEs and AEs That Are Related to Vaccination or That Led to Discontinuation:***

At any time during the study, a subject who experiences an SAE or an AE must be followed if *either* of the following is true:

- The SAE or AE is considered by the Investigator to be related to vaccination, and is not resolved by the end of the subject's participation in the trial
- The subject has been discontinued from the trial because of the SAE or AE

Any such subject must be followed until the condition resolves, becomes stable, or becomes chronic.

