4.3.2.3.3 Unsolicited Non-serious Adverse Events From Day 0 to Visit 2 After Vaccination

In addition to recording solicited reactions, subjects will be instructed to record any other medical events that may occur between Visit 1 and Visit 2 after vaccination. Space will be provided in the DC for this purpose.

For each unsolicited non-serious AE, the following information is to be recorded:

- Start and stop dates^a
- Intensity of the event:
 - For measurable unsolicited non-serious AEs that are part of the list of solicited reactions, the size of the AE as well as the temperature for fever will be collected and analyzed based on the corresponding scale used for solicited reactions (see [Table 4.1](#) and [Table 4.2](#)).
 - Other unsolicited non-serious AEs will be classified according to the following intensity scale:
 - Grade 1: No interference with activity
 - Grade 2: Some interference with activity
 - Grade 3: Significant; prevents daily activity
- Action taken for each AE, if any (e.g., medication)

The action taken by the subject to treat any **unsolicited AEs** will be classified in the CRF using the following scale:

- 0: None
- 1: Medication (self-medication with an existing prescription or over-the-counter medication)
- 2: Health care provider contact (no new medication prescribed)
- 3: Health care provider contact and prescription of a new medication (health care provider instructed subject to take a new medication, either an over-the-counter medication or one requiring a written prescription)

^a The stop date of all related AEs will be actively solicited. For other events, the investigator will provide the stop date when it becomes available. AEs for which no stop date was obtained during the course of the trial will be considered as ongoing at the end of the trial.

- Whether the AE led to discontinuation
- Whether the AE was related to vaccination (for unsolicited systemic AEs)

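### Stop dates are actively sought only for related AEs, so longer not-related AEs still open at Visit 2 tend to drop out of the duration summaries, and an unknown end is labelled ongoing

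*Protocol*

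**What the plan says.** Protocol 9.3.2.3.3 opens its data list with "For each unsolicited non-serious AE, the following information is to be recorded", and start and stop dates come first. Footnote a then splits the effort by causality: "The stop date of all related AEs will be actively solicited. For other events, the investigator will provide the stop date when it becomes available". It closes with a default: "AEs for which no stop date was obtained during the course of the trial will be considered as ongoing at the end of the trial". SAP 4.3.2.3.3 carries the same footnote, so this is the current rule in both documents.

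Duration is a listed endpoint for all unsolicited AEs up to Visit 2, related or not (Protocol 9.3.2.2, SAP 4.3.2.2, SAP Table 5.2).

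At Visit 2, "the Investigator or a delegate will ask the subject about any solicited reactions and unsolicited AEs recorded in the DC" (Protocol 9.3.2.3), and gaps in the diary are clarified verbally with the subject (Protocol 13.2). Neither step depends on relatedness.

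After Visit 2, the memory aid and Telephone Call 2 cover SAEs and MAAEs (Protocol 5.1.3 and the notes to the Table of Study Procedures). The instruction for the call in 5.1.4 begins "Review the MA and ask the subject if he/she has experienced any SAE in the time since vaccination" and adds MAAEs; it does not mention AEs left open at Visit 2.

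In the analysis, a missing stop date stays missing (SAP 5.3.1.5), and a missing stop date makes the duration missing (SAP 4.4.2.2.5).

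**The concern.** The endpoint applies to every unsolicited AE, but the effort to complete it depends on the causality judgement. A not-related AE that has ended by Visit 2 yields a duration. One that is still open yields a duration only if the stop date happens to reach the site later. Whether a duration is observed thus depends on how long the event lasted, which is informative missingness.

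Two outputs suffer. The duration summary for not-related AEs is weighted towards short events. And any count or listing of AEs ongoing at the end of the trial mixes events that truly had not resolved with events whose end was never established. The end of the trial is the last subject's safety call, 180 to 194 days after vaccination (Protocol 5.1.5). The label therefore asserts a status months after the last scheduled question about that AE.

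**Working it through.** **1. Where the gap lies.** Related AEs have their stop dates solicited. SAEs and AEs leading to discontinuation have their own follow-up (Protocol 5.1.4 and section 10). AEs over by Visit 2 are covered by the diary review. That leaves not-related, non-serious unsolicited AEs, not leading to discontinuation, still open at Visit 2. Protocol 11.1 mentions a 6-month questionnaire on SAEs and AEs of particular interest, if applicable, but 9.3.2.3.5 says AEs of special interest are not applicable. No scheduled contact covers this remainder.

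**2. Direction of the bias.** SAP 4.4.2.2.5 gives duration = stop date − start date + 1. If a not-related AE's stop date is known only when it falls by Visit 2, the longest observable duration is Visit 2 day − start day + 1. For an AE starting on D20 with Visit 2 on D30, this is 30 − 20 + 1 = 11 days. The most it can ever be is 44 − 0 + 1 = 45 days. Take an AE that starts on D29, is open at a Visit 2 on D35 and ends on D40. It truly lasts 40 − 29 + 1 = 12 days. Without a later date it is labelled ongoing and its duration is missing. Losses fall on the longer events, so observed durations are too short.

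**3. Possible size.** The plan states no figure to reproduce, and gives neither AE durations nor rates of missing dates. The following simulation of 400,000 AEs rests wholly on assumptions:

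- onset uniform over D0 to D30;
- Visit 2 uniform over D30 to D44;
- end of follow-up D180 to D194;
- lognormal duration, rounded up to whole days;
- q = chance that the stop date is obtained for a not-related AE open at Visit 2 and over by the end of follow-up.

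| Assumed median (days) / log-scale SD | Open at Visit 2 | Mean duration (days) if all dates sought (q = 1) | Observed mean, q = 0 to 0.75 | Truly unresolved at end | Labelled ongoing, q = 0 to 0.75 |
|---|---|---|---|---|---|
| 5 / 1.0 | 11.1% | 8.7 | 6.5 to 8.2 | 0.0% | 11.1% to 2.8% |
| 7 / 1.2 | 20.9% | 13.9 | 7.6 to 12.6 | 0.4% | 20.9% to 5.5% |
| 14 / 1.2 | 38.3% | 24.3 | 10.3 to 21.9 | 1.8% | 38.3% to 10.9% |

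The smallest shortfall in the mean is (8.7 − 8.2)/8.7 = 6%; the largest is (24.3 − 10.3)/24.3 = 58%. Medians move less: at q = 0 they are 5 against 6, 6 against 7 and 8 against 14 days. SAP Table 5.1 lists only counts and percentages for clinical safety, so the mean is just a gauge; in categorical tables the longer duration categories would be depleted.

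**4. Subjects who could be touched.** With 450 subjects per arm, assume that 20% to 35% have an unsolicited AE, that 80% to 95% of these have one judged not related, and that 10% to 25% of those are open at Visit 2. Then 450 × 0.20 × 0.80 × 0.10 = 7.2 and 450 × 0.35 × 0.95 × 0.25 = 37.4, or about 7 to 37 per arm. This is an upper range under those assumptions: it supposes that no date arrives after Visit 2, and it counts AEs that truly remain ongoing.

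**The case against.** The strongest reply is that concentrating follow-up on related AEs is a deliberate choice, stated identically in both documents. Stop dates are required for each AE, all recorded AEs are reviewed at Visit 2, diary gaps are queried, and the Investigator must explain missing information (Protocol 11.1) and supply a not-related AE's stop date when it becomes available. Dates asked for at about D180 would also rely on recall. All of this stands, and it narrows the gap to AEs open at Visit 2. It does not close the gap, because nothing schedules the question afterwards.

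Several stronger readings are tempting but unsupported.

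- A reader might infer that an AE labelled ongoing is analysed as lasting to month 6. SAP 4.4.2.2.5 and 5.3.1.5 leave duration and stop date missing, so the bias runs the other way.
- A reader might infer that not-related AEs are never asked about. The Visit 2 review contradicts this.
- A reader might take the follow-up rule in 5.1.4 as barring follow-up of not-related AEs after Visit 2. Its relatedness condition reads "The SAE or AE is considered by the Investigator to be related to vaccination, and is not resolved by the end" of the subject's participation, which lasts 180 to 194 days (Synopsis). It concerns follow-up beyond the trial, not the interval from Visit 2 to the call.
- A reader might assume a planned comparison of duration or resolution by relatedness. Protocol 12.1.3 and SAP Table 5.2 list relationship and duration as descriptors and state no such cross-table. Outcome is an endpoint only for SAEs and for MAAEs after Visit 2.
- A reader might infer a biased comparison of the vaccines. The Investigator who judges causality is blinded (Protocol 6.4) and the rule is the same in both groups. Some effect remains possible if the share of AEs called related differs by group; injection site AEs, for instance, are related by convention (Protocol 9.3.2.3.7).

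**Conclusion.** The point holds in a limited form. For not-related, non-serious unsolicited AEs still open at Visit 2, no scheduled contact asks for the stop date. Under the SAP the duration is then missing, preferentially for longer events, so observed durations of not-related AEs are biased downwards. The default label merges an unknown end with true non-resolution. The footnote and SAP 5.3.1.5 also handle the same missing date differently: one assigns a status, the other leaves it missing.

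The size is not derivable from the documents. The simulated 6% to 58% shortfall depends on the assumed durations and on q, and disappears at q = 1. Only descriptive safety data are affected; the primary non-inferiority analysis is untouched. This is a cheap improvement to the collection of a listed endpoint, not a threat to the trial's conclusions.

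**What to change.** 1. In Protocol 5.1.4, add to Telephone Call 2: for every unsolicited AE open at Visit 2, whatever its relationship to vaccination, ask for the stop date or whether it is still ongoing. Update the Table of Study Procedures and SAP Table 3.2 to match.
2. In footnote a of Protocol 9.3.2.3.3 and SAP 4.3.2.3.3, replace the default so that an AE is recorded as ongoing only if confirmed at that contact, and otherwise its end is recorded as unknown.
3. In the SAP, report the number of AEs with missing duration by group and relatedness.
4. Align the footnote with SAP 5.3.1.5, so that one rule governs an AE without a stop date.

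The cost is one question at a call already scheduled, only for subjects with an open AE, plus wording changes in both documents. The downside is a few minutes of site time and some dates given from memory.
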